## 7.4 Concomitant Medications, Treatments, and Procedures

All concomitant prescription medications taken during study participation will be recorded on the case report forms (CRFs). For this protocol, a prescription medication is defined as a medication that can be prescribed only by a properly authorized/licensed clinician. Medications to be reported in the CRF are concomitant prescription medications, over-the-counter medications and non-prescription medications.

# 8 Assessment of Safety

## 8.1 Specification of Safety Parameters

Ferumoxytol injection is lawfully marketed in the US and is being administered according to FDA-approved prescribing information. The PI will serve as the medical monitor for the study. Subjects will be observed for known treatment-related adverse events as described in the prescribing information including evidence of hypersensitivity for 30 minutes after infusion of ferumoxytol injection.

CONFIDENTIAL

This material is the property of the NYU School of Medicine and Langone Medical Center. Do not disclose or use except as authorized in writing by the study sponsor  
Interventional Template Version: 28 APR 2017

### 8.1.1 Definition of Adverse Events (AE)

An **adverse event** (AE) is any symptom, sign, illness or experience that develops or worsens in severity during the course of the study. Intercurrent illnesses or injuries should be regarded as adverse events. Abnormal results of diagnostic procedures are considered to be adverse events if the abnormality:

- results in study withdrawal
- is associated with a serious adverse event
- is associated with clinical signs or symptoms
- leads to additional treatment or to further diagnostic tests
- is considered by the investigator to be of clinical significance

### 8.1.2 Definition of Serious Adverse Events (SAE)

#### Serious Adverse Event

Adverse events are classified as serious or non-serious. A **serious adverse event** is any AE that is:

- fatal
- life-threatening
- requires or prolongs hospital stay
- results in persistent or significant disability or incapacity
- a congenital anomaly or birth defect
- an important medical event

Important medical events are those that may not be immediately life threatening, but are clearly of major clinical significance. They may jeopardize the subject, and may require intervention to prevent one of the other serious outcomes noted above. For example, drug overdose or abuse, a seizure that did not result in in-patient hospitalization, or intensive treatment of bronchospasm in an emergency department would typically be considered serious.

All adverse events that do not meet any of the criteria for serious should be regarded as **non-serious adverse events**.

### 8.1.3 Definition of Unanticipated Problems (UP)

#### Unanticipated Problems Involving Risk to Subjects or Others

Any incident, experience, or outcome that meets all of the following criteria:

CONFIDENTIAL

This material is the property of the NYU School of Medicine and Langone Medical Center. Do not disclose or use except as authorized in writing by the study sponsor  
Interventional Template Version: 28 APR 2017

- Unexpected in nature, severity, or frequency (i.e. not described in study-related documents such as the IRB-approved protocol or consent form, the investigators brochure, etc)
- Related or possibly related to participation in the research (i.e. possibly related means there is a reasonable possibility that the incident experience, or outcome may have been caused by the procedures involved in the research)
- Suggests that the research places subjects or others at greater risk of harm (including physical, psychological, economic, or social harm).

## 8.2 Classification of an Adverse Event

### 8.2.1 Severity of Event

For AEs not included in the protocol defined grading system, the following guidelines will be used to describe severity.

- **Mild** – Events require minimal or no treatment and do not interfere with the participant's daily activities.
- **Moderate** – Events result in a low level of inconvenience or concern with the therapeutic measures. Moderate events may cause some interference with functioning.
- **Severe** – Events interrupt a participant's usual daily activity and may require systemic drug therapy or other treatment. Severe events are usually potentially life-threatening or incapacitating.

### 8.2.2 Relationship to Study Agent

The clinician's assessment of an AE's relationship to study agent (drug, biologic, device) is part of the documentation process, but it is not a factor in determining what is or is not reported in the study. If there is any doubt as to whether a clinical observation is an AE, the event will be reported.

For all collected AEs, the clinician who examines and evaluates the participant will determine the AE's causality based on temporal relationship and his/her clinical judgment. The degree of certainty about causality will be graded using the categories below.

- **Definitely Related** – There is clear evidence to suggest a causal relationship, and other possible contributing factors can be ruled out. The clinical event, including an abnormal laboratory test result, occurs in a plausible time relationship to drug administration and cannot be explained by concurrent disease or other drugs or chemicals. The response to withdrawal of the drug (dechallenge) should be clinically plausible. The event must be pharmacologically or phenomenologically definitive, with use of a satisfactory rechallenge procedure if necessary.
- **Probably Related** – There is evidence to suggest a causal relationship, and the influence of other factors is unlikely. The clinical event, including an abnormal laboratory test result, occurs within a reasonable time after administration of the drug, is unlikely to be attributed to concurrent disease or other drugs or chemicals, and follows a clinically reasonable response on withdrawal (dechallenge). Rechallenge information is not required to fulfill this definition.
- **Possibly Related** – There is some evidence to suggest a causal relationship (e.g., the event occurred within a reasonable time after administration of the trial medication). However, other factors may have contributed to the event (e.g., the participant's clinical condition,

CONFIDENTIAL

other concomitant events). Although an AE may rate only as “possibly related” soon after discovery, it can be flagged as requiring more information and later be upgraded to “probably related” or “definitely related,” as appropriate.

- **Unlikely to be related** – A clinical event, including an abnormal laboratory test result, whose temporal relationship to drug administration makes a causal relationship improbable (e.g., the event did not occur within a reasonable time after administration of the trial medication) and in which other drugs or chemicals or underlying disease provides plausible explanations (e.g., the participant’s clinical condition, other concomitant treatments).
- **Not Related** – The AE is completely independent of study drug administration, and/or evidence exists that the event is definitely related to another etiology. There must be an alternative, definitive etiology documented by the clinician.

### 8.2.3 Expectedness

The principal investigator or an appropriately licensed Co-investigator will be responsible for determining whether an AE is expected or unexpected. An AE will be considered unexpected if the nature, severity, or frequency of the event is not consistent with the risk information previously described for the study agent.

## 8.3 Time Period and Frequency for Event Assessment and Follow-Up

The occurrence of an AE or SAE may come to the attention of study personnel during study visits and interviews of a study participant presenting for medical care, or upon review by a study monitor. All AEs including local and systemic reactions not meeting the criteria for SAEs will be captured on the appropriate RF. Information to be collected includes event description, time of onset, clinician’s assessment of severity, relationship to study product (assessed only by those with the training and authority to make a diagnosis), and time of resolution/stabilization of the event. All AEs occurring while on study must be documented appropriately regardless of relationship. All AEs will be followed to adequate resolution.

Any medical condition that is present at the time that the participant is screened will be considered as baseline and not reported as an AE. However, if the study participant’s condition deteriorates at any time during the study, it will be recorded as an AE. UPs will be recorded in the data collection system throughout the study.

Changes in the severity of an AE will be documented to allow an assessment of the duration of the event at each level of severity to be performed. AEs characterized as intermittent require documentation of onset and duration of each episode.

The PI will record all reportable events with start dates occurring any time after informed consent is obtained until 7 (for non-serious AEs) or 30 days (for SAEs) after the last day of study participation. At each study visit, the investigator will inquire about the occurrence of AE/SAEs since the last visit. Events will be followed for outcome information until resolution or stabilization.

All unresolved adverse events should be followed by the investigator until the events are resolved, the subject is lost to follow-up, or the adverse event is otherwise explained. At the last scheduled visit, the investigator should instruct each subject to report any subsequent event(s) that the subject, or the subject’s personal physician, believes might reasonably be related to participation in this study. The investigator should notify the study sponsor of any death or adverse event occurring at any time after a subject has discontinued or terminated study participation that may

CONFIDENTIAL

This material is the property of the NYU School of Medicine and Langone Medical Center. Do not disclose or use except as authorized in writing by the study sponsor  
Interventional Template Version: 28 APR 2017

reasonably be related to this study. The sponsor should also be notified if the investigator should become aware of the development of cancer or of a congenital anomaly in a subsequently conceived offspring of a subject that has participated in this study.

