## Schematic of Study Design

## Schedule of Assessments

| Visit Name                  | Screening   | First Dose Ferumoxytol injection | Second Dose Ferumoxytol injection
(3-8 days after first dose) |
|-----------------------------|-------------|----------------------------------|--|
| Visit Number                | 1           | 2                                | 3  |
| Study Week ( $\pm 7$ days)* | 0           | 0-2                              | 1-3  |
| Informed consent            | X           |                                  |  |
| Screening Evaluation        | X           |                                  |  |
| Medical History             | X           | X                                | X  |
| Bleeding/Blood History      | Transfusion | X                                | X  |

CONFIDENTIAL

This material is the property of the NYU School of Medicine and Langone Medical Center. Do not disclose or use except as authorized in writing by the study sponsor  
Interventional Template Version: 28 APR 2017

|                                |           |   |   |
|--------------------------------|-----------|---|---|
| Vital Signs                    | X         | X | X |
| Cardiovascular exam            | X         | X | X |
| VAD settings                   | X         | X | X |
| Ferumoxytol
Administration* | injection | X | X |
| Infusion Monitoring            |           | X | X |
| AE monitoring                  |           | X | X |
| Concomitant Meds               | X         | X | X |

\*Ferumoxytol injection will be administered according to FDA-approved prescribing instructions 3-8 days apart

CONFIDENTIAL

This material is the property of the NYU School of Medicine and Langone Medical Center. Do not disclose or use except as authorized in writing by the study sponsor  
Interventional Template Version: 28 APR 2017

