# **7 Study Procedures and Schedule**

## **7.1 Study Procedures/Evaluations**

### **7.1.1 Study Specific Procedures**

Study visits (See Attached Study Schematic Figure and Schedule of Assessments Table): The study will require 3 visits over approximately 2 weeks for each subject.

- Visit 1: Informed consent and screening\*
- Visit 2: First dose of ferumoxytol injection Study Drug\*
- Visit 3: Second dose of ferumoxytol injection Study Drug

\*Visits 1 and 2 may occur on the same day.

Screening procedures. After the informed consent form is signed, chart review and patient interview will be performed to determine eligibility. Screening will include subject interview and chart review to determine eligibility. Clinical information on co-morbid conditions, VAD settings, and concomitant medications will be collected. Vital signs in the seated position and a brief cardiovascular exam will be recorded. Women of childbearing potential will undergo urine or blood pregnancy testing.

Study Drug Administration: Ferumoxytol injection will be administered to eligible subjects according to FDA-approved prescribing information. Prior to administration, interim history, concomitant medications, VAD settings, vital signs and a cardiovascular exam will be recorded. Two doses of ferumoxytol injection will be administered: an initial 510 mg dose followed by a second 510 mg dose 3 to 8 days later, each dose given as an intravenous infusion in 50-200 mL 0.9% Sodium Chloride Injection, USP or 5% Dextrose Injection, USP while the subject is in a reclined or semi-reclined position. Subjects will be observed for signs or symptoms of hypersensitivity reactions (including monitoring of blood pressure and pulse rate) during and for at least 30 minutes after ferumoxytol injection administration. The dose, date and time of infusion, duration of infusion, and treatment-related adverse effects (diarrhea, nausea, dizziness, hypotension, hypersensitivity) will be recorded.

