### 7.3.3 Final Study Visit

#### Enrollment/Baseline Visit (Visit 3, Day 3-8)

- Verify informed consent documentation.
- Verify inclusion/exclusion criteria.
- Assess for interim changes in clinical status or concomitant medications.
- Record VAD settings, seated vital signs (mean blood pressure, heart rate, oxygen saturation) and cardiovascular examination.
- Obtain urine or blood pregnancy test in women of childbearing potential.
- Record vital signs and assess clinical stability of subject.
- Administer the study treatment as described with monitoring for hypersensitivity reactions.
- Report status of iron repletion to clinical care team.

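### No adverse-event inquiry is scheduled after the last infusion, so the incidence of treatment-related adverse events may be under-counted

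*Combined protocol and SAP*

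**What the plan says.** - **Endpoint.** Sections 4.2.2 and 9.4.1 name the incidence of treatment-related AEs as the primary safety endpoint. Section 9.2 attaches no hypothesis to it. The aim there is to estimate treatment risk for planning later trials.
- **Active inquiry.** Section 8.3: "At each study visit, the investigator will inquire about the occurrence of AE/SAEs since the last visit". In the Schedule of Assessments, the row "AE monitoring" is marked only at the two infusion visits. Sections 7.1.1 and 7.3.3 make Visit 3 both the second infusion and the final visit, at Day 3-8.
- **Observation.** Section 7.1.1 has subjects watched for hypersensitivity "during and for at least 30 minutes after ferumoxytol injection administration". Section 8.1 covers known treatment-related events, "including evidence of hypersensitivity for 30 minutes after infusion of ferumoxytol injection".
- **Afterwards.** Section 5.5 leaves only extraction from the medical record. Section 7.3.4 requires no visit on early termination. Besides study visits, section 8.3 names as sources of AE information "interviews of a study participant presenting for medical care, or upon review by a study monitor". At the last visit the investigator asks subjects to report later events that they or their own physician think may be related.
- **Recording window.** Section 8.3 has events recorded "until 7 (for non-serious AEs) or 30 days (for SAEs) after the last day of study participation".
- **Chart items.** Section 7.1.1 lists laboratory values and bleeding or transfusion data from week 2 to week 24, and six-minute walk results. The Protocol Summary adds hospitalizations. No general AE item is listed.

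**The concern.** The recording window says which events count. It does not say how study staff will learn of them. For delayed events after the first infusion there is a method: the investigator asks at the next visit. After the last infusion there is no next visit. The same holds for a patient who receives only the first dose, because the visit that would carry the look-back does not take place.

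Any error from incomplete capture runs one way, towards a lower incidence. Serious events are likely to surface through hospital or clinic care, so mild and moderate events are the ones most exposed. What is at stake is the safety estimate that the pilot is meant to hand on, in a population for which section 2.1 reports no published ferumoxytol data.

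**Working it through.** The plan gives no figure for AE capture, so there is none to reproduce. The check sets out the scheduled coverage, then illustrates what a gap could do.

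**1. Scheduled coverage**

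| | After first infusion, second given | After last infusion |
|---|---|---|
| Direct observation | at least 0.5 h | at least 0.5 h |
| Scheduled AE inquiry | one, at Visit 3 | none |
| Look-back covered | 3 to 8 days = 72 to 192 h | none beyond observation |

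The 72 to 192 h range takes the second dose at Day 3-8 (section 7.3.3). Section 5.7.1 refers to a return within 15 days (360 h), and section 7.3 gives visits a window of ±7 days (8 + 7 = Day 15), while section 6.1.7 bars delay outside the labeling. These passages need reconciling. The zero in the last column does not depend on which applies.

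**2. Illustration; every input is assumed**

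Let q be the AE risk per infusion, f the share of events starting after observation ends, and c the share of late events after the second dose that passive routes find. Assume that risks at the two infusions are independent within a patient, that everyone receives both doses with the second on Day 3-8, and that Visit 3 finds all first-dose events.

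- True incidence = 1 − (1 − q)²
- Shortfall = (1 − q) × q × f × (1 − c)

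At q = 0.05, f = 0.5, c = 0: true = 1 − 0.95² = 0.0975; shortfall = 0.95 × 0.05 × 0.5 = 0.02375; recorded = 0.07375.

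| q (f = 0.5) | True | Recorded, c = 0 | Recorded, c = 0.5 | Recorded, c = 1 | Patients missed of 20 (c = 0; c = 0.5) |
|---|---|---|---|---|---|
| 2% | 3.96% | 2.98% | 3.47% | 3.96% | 0.20; 0.10 |
| 5% | 9.75% | 7.4% | 8.6% | 9.75% | 0.48; 0.24 |
| 10% | 19.0% | 14.5% | 16.75% | 19.0% | 0.90; 0.45 |

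With c = 0 and f from 0.25 to 0.75, the shortfall is 0.49 to 1.47 percentage points at q = 2%, 1.19 to 3.56 at 5%, and 2.25 to 6.75 at 10%.

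The range for q is a choice. Section 2.4.1 reports single-reaction rates of 1.9% (33/1,726) and 3.7% (63/1,726), but per subject and mainly in chronic kidney disease.

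Independence matters. The term (1 − q) × q is the chance of reacting to the second dose only. Positive within-patient correlation makes it smaller. If the same patients react to both doses and all first-dose events are found, the shortfall is zero.

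For scale, the exact 95% confidence interval for 2 of 20 patients is 1.2% to 31.7%.

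**3. Recording window**

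The last day of participation is not defined. The Protocol Summary (six months' duration) and section 8.4.4 (six-month follow-up) point to month 6. Section 5.5 ties active participation to the visits.

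| Last day taken as | Non-serious recording ends | SAE recording ends |
|---|---|---|
| Visit 3, Day 3-8 | Day 10-15 | Day 33-38 |
| 182 days after the last infusion | Day 192-197 | Day 215-220 |

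A Visit 3 on Day 15 would give Days 22 and 45, or Days 204 and 227. The readings differ by 182 days. On the first reading, the non-serious window closes 7 days after the last infusion; the week-2 chart items, if counted from that infusion, start at day 14. Neither reading adds an inquiry.

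**The case against.** The strongest reply is that existing capture suits this endpoint. Only treatment-related events count, and the closing instruction in section 8.3 asks subjects to report just such events. Section 8.3 also requires all AEs on study to be documented. Section 5.4 describes one dedicated team seeing these patients regularly, and section 5.5 does not confine chart review to the listed items. Safety is descriptive, and the illustrated loss is under one patient in 20.

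Much of this stands. These routes could make the shortfall nil, and the sampling error at n = 20 is far larger than the illustrated loss. But none of them is a scheduled question. Self-report also makes the subject or personal physician the first judge of causality, a task that section 8.2.2 gives to the examining clinician.

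Two stronger arguments may tempt a reader:

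- Section 7.1.1 says "treatment-related adverse effects (diarrhea, nausea, dizziness, hypotension, hypersensitivity) will be recorded", and that list is shorter than the common reactions in section 2.4.1. One might infer that the others go unrecorded. Section 8.1 refers to known events in the prescribing information and section 8.3 to all AEs, so the list does not limit capture.
- The half-life in section 2.2.1 might suggest that most delayed events fall after observation. The documents do not link AE onset to plasma level, and they describe elimination as capacity-limited.

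**Conclusion.** The concern holds as a gap in scheduled ascertainment. After each patient's last infusion, delayed events reach the primary safety endpoint only through passive routes or chart extraction, so overall incidence may be under-counted, mainly for non-serious events. The gap follows from the visit schedule and needs no assumption. Its effect does: the size cannot be derived from the documents and ranges from zero upward. In the illustration it is 0 to 0.9 patient of 20 at f = 0.5, given independent risks, full detection of first-dose events and a second dose on Day 3-8. The feasibility test and the sample size are unaffected.

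Three further inferences are not supported:

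- That events will certainly be missed. Passive capture may be complete.
- That a comparison between doses is compromised. The plan contains none.
- That SAE recording stops about a month after Visit 3. The six-month duration in the Protocol Summary favors the longer reading; the fault is that the text leaves it open.

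The conditions on the safety set in section 9.3 are a separate, minor matter.

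**What to change.** 1. Schedule one AE telephone inquiry by existing staff about 7 days after each patient's last infusion. Include patients who do not receive the second dose, with permission if they have withdrawn, as section 5.7.2 already requires for chart extraction.
2. Add AEs and SAEs from the first infusion onward as an item in the planned chart abstraction.
3. Define the last day of study participation in section 8.3 by reconciling it with the Protocol Summary, section 5.5 and section 8.4.4, without shortening SAE recording.
4. Bring the Key Procedures entry of the Protocol Summary, the Schedule of Assessments and sections 5.5, 7.1.1 and 8.3 into line.

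The cost is about 20 short calls, one abstraction item, and an amendment with IRB review and a re-consent determination under section 12.2. The reported AE rate may be higher as a result. Dosing and clinical management are untouched.
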